4.14	ALGORITHMS/SAS CODES	58
5	TABLES AND LISTINGS	66
5.1	TABLE FORMAT	66
	Headers	66
	Display Titles	67
5.2	CONVENTIONS	67
5.3	TABLES	69
5.3.1	Section 14.1: Demographic and Baseline	69
5.3.2	Section 14.2: Primary	69
5.3.3	Section 14.2: Secondary	70
5.3.4	Section 14.3: Safety	71
5.4	LISTINGS	72
5.5	FIGURES	74
5.6	REFERENCES	75
APPENDIX 1:	CCI QUESTIONNAIRE	76
APPENDIX 2:	CCI QUESTIONNAIRE CCI	82
APPENDIX 3:	WHO-DD PREFERRED TERMS FOR ANTIBIOTICS AND ANTI-PSEUDOMONAL ANTIBIOTICS	91
APPENDIX 4:	MACRO CODE FOR NON-PARAMETRIC ANCOVA	94

CONFIDENTIAL

Sponsor:	Zambon S.p.A.	Protocol Number:	Z7224L01
----------	---------------	------------------	----------

Abbreviations

CCI	CCI
ADaM	Analysis Data Model
AE	Adverse Event
ANCOVA	Analysis of Covariance
ATC	Anatomical Therapeutic Chemical
BMI	Body Mass Index
CA	Competent Authority
CF	Cystic Fibrosis
CFU	Colony Forming Units
CI	Confidence Interval
CRO	Contract Research Organisation
CS	Clinically Significant
CT	Computerised Tomography
CTP	Clinical Trial Protocol
CTR	Clinical Trial Report
CCI	Data CCI
EC	Ethics Committee
eCRF	electronic Case Report Form
eCOA	electronic Clinical Outcome Assessment
ED	Exposure Day
FEV ₁	Forced Expiratory Volume in one second
FOE	Frequency of Exacerbations
FVC	Forced Vital Capacity
GLI	Global Lung Function Initiative
ICH	International Conference on Harmonisation
IMP	Investigational Medicinal Product
ITT	Intention-To-Treat
IWRS	Interactive Web Response System
MAR	Missing At Random
MedDRA	Medical Dictionary for Regulatory Activities
MI	Multiple Imputation
mITT	Modified Intention-To-Treat (Full Analysis Set)
MIU	Million International Unit
NCFB	Non-CF-Bronchiectasis
NCS	Non Clinically Significant
P. aeruginosa	Pseudomonas aeruginosa
PP	Per-Protocol
PT	Preferred Term
PWP	Prentice, Williams and Peterson
CCI	
SAE	Serious Adverse Event
SAP	Statistical Analysis Plan

CONFIDENTIAL

Sponsor:	Zambon S.p.A.	Protocol Number:	Z7224L01
----------	---------------	------------------	----------

SD	Standard Deviation
CCI	
SOC	System Organ Class
SUSAR	Suspected Unexpected Serious Adverse Reaction
TEAE	Treatment Emergent Adverse Event
WHO	World Health Organisation
WHO-DD	WHO Drug Dictionary

CONFIDENTIAL

Sponsor:	Zambon S.p.A.	Protocol Number:	Z7224L01
----------	---------------	------------------	----------

1 Introduction

This document presents the Statistical Analysis Plan (SAP) for Zambon, Protocol No. Z7224L01: A double-blind, placebo-controlled, multi-centre, clinical trial to investigate the efficacy and safety of 12 months of therapy with inhaled colistimethate sodium in the treatment of subjects with non-cystic fibrosis bronchiectasis chronically infected with *Pseudomonas aeruginosa* (*P. aeruginosa*)

This analysis plan is based on the final protocol Version 7.0 dated 22Oct2019.

The SAP provides the description of the analysis for the final analyses. Any deviations from the SAP which occur after breaking the blind will be documented and justified in the final clinical trial report (CTR) and deviations will be clearly marked as 'post hoc' analysis.

CONFIDENTIAL

Sponsor:	Zambon S.p.A.	Protocol Number:	Z7224L01
----------	---------------	------------------	----------

2 Study Objectives

The primary objective of the trial is to investigate the effect of the use of inhaled colistimethate sodium, administered twice daily via the **CCI** for 12 months, compared to placebo in subjects with non-cystic fibrosis bronchiectasis (NCFB) chronically infected with *P. aeruginosa* on the annualized frequency of pulmonary exacerbations.

2.1 Primary Endpoint

The primary endpoint of this trial is the mean annual NCFB pulmonary exacerbation rate.

A pulmonary exacerbation is defined as the presence concurrently of at least 3 of the following 8 symptoms/signs for at least 24 hours:

- increased cough;
- increased sputum volume and/or consistency;
- increased sputum purulence;
- new or increased haemoptysis;
- increased wheezing;
- increased dyspnoea;
- increased fatigue/malaise;
- episodes of fever (temperature $\geq 38^{\circ}\text{C}$);

And it is clinically determined that the subject requires and is prescribed systemic antibiotic therapy.

The start date of a protocol-defined pulmonary exacerbation will be taken as the first day that at least 3 of the pre-defined 8 symptoms/signs occurred concurrently for at least 24 hours, as determined by the Investigator, as documented by the start date of the corresponding AE in the eCRF AE form.

Resolution of a pulmonary exacerbation is defined as the date of completion of the required course(s) of systemic antibiotic treatment and/or the Investigator's judgement that the NCFB pulmonary exacerbation has resolved, as documented by the end date provided for the corresponding AE in the eCRF AE form, whichever is the later of the two dates. The exacerbation end date will be reported at the next scheduled visit or by phone. A new pulmonary exacerbation is only considered to occur if there are at least 14 days between the end of the course of systemic antibiotics and the onset of new qualifying symptoms.

The treatment of pulmonary exacerbations will follow current treatment regimens used at the respective participating investigational site.

A supportive analysis will be conducted using an alternative definition of NCFB pulmonary exacerbation. The re-classification of exacerbations will be done in a blinded fashion (before

CONFIDENTIAL

Sponsor:	Zambon S.p.A.	Protocol Number:	Z7224L01
----------	---------------	------------------	----------

database lock). Alternative definition of pulmonary exacerbation: deterioration in three or more of the following key symptoms for at least 48 hours:

- Cough;
- Sputum volume and/or consistency;
- Sputum purulence;
- Breathlessness and/or exercise tolerance (dyspnoea);
- Fatigue and/or malaise;
- Haemoptysis;

And a physician determines a change in bronchiectasis treatment is required when other potential causes of clinical deterioration have been discounted.

2.2 Secondary Endpoints

The secondary endpoints of this trial are:

- CCI [REDACTED]
- [REDACTED]
- [REDACTED]
- [REDACTED]
- [REDACTED]
- [REDACTED]
- [REDACTED]
- [REDACTED]
- [REDACTED]

CONFIDENTIAL

Sponsor:	Zambon S.p.A.	Protocol Number:	Z7224L01
----------	---------------	------------------	----------

2.3 Safety Endpoints

The safety endpoints of this trial are:

- incidence of treatment emergent adverse events (TEAEs);
- absolute changes in percent-predicted forced expiratory volume in 1 second (FEV₁) from baseline to each post-baseline visit;
- the number of subjects experiencing bronchospasm clinically or spirometrically determined following IMP administration;
- CCI [REDACTED] from Screening/Randomisation (Visit 1/Visit 2) to Visits 3, 5 and end of treatment (Visit 7) as well as on sputum from Exacerbation Visits and clinic visits due to pneumonia;
- CCI [REDACTED] from Screening (Visit 1) to End of Treatment (Visit 7);
- haematology, clinical chemistry and renal function tests;
- physical examination and vital signs data;
- 12-lead electrocardiogram.

CONFIDENTIAL

Sponsor:	Zambon S.p.A.	Protocol Number:	Z7224L01
----------	---------------	------------------	----------

3 Study Design

3.1 Discussion of Study Design

This is a randomised, multi-centre, double-blind, placebo-controlled, parallel-group interventional trial in subjects with NCFB suffering from chronic infections with *P. aeruginosa*.

The trial will be conducted in approximately 100 sites in up to 15 countries. A total of 420 subjects (210 in each treatment group) are planned to be enrolled into the trial. The enrolment is competitive among sites.

At Visit 2 (within 30 days after Visit 1), eligible subjects with *P. aeruginosa* cultured from an initial sputum sample will be randomised in a 1:1 ratio to receive either colistimethate sodium or placebo.

It is planned that subjects will be contacted by phone 7 days after Randomisation (Visit 2) to determine if there are any issues with IMP administration and/or any initial AEs and will, thereafter, attend 5 further visits at the sites at 1, 3, 6, 9, and 12 months after Randomisation (i.e. Visits 3, 4, 5, 6, and 7) and will have 1 follow-up phone call at 12.5 months. Additional clinic visits, where feasible, and weekly phone calls will be conducted following pulmonary exacerbations until resolution.

The maximum expected duration of participation in the trial for an individual subject, from Visit 1 (Screening) to the follow-up phone call is up to 13.5 months. Treatment duration will be 12 months.

The start of the trial is defined as first subject in, i.e. Visit 1 for the first subject. The end of the trial is defined as the last subject out, i.e. when the last subject has the follow-up phone call.

3.2 Study Treatment

At Visit 2 (within 30 days after Visit 1) eligible subjects with *P. aeruginosa* cultured from their initial sputum sample will be randomised in a 1:1 ratio to receive either colistimethate sodium or placebo.

Subjects will be administered the first dose of the IMP at the investigational site prepared by the site staff and will be instructed by the Investigator or a delegated person how to prepare and self-administer the IMP at home via the **CCI CCI** Aerosol Delivery **CCI** system, twice daily (morning and evening) over a period of 12 months. Prior to each administration, a bronchodilator (salbutamol/albuterol) should be taken; if the subject prefers not to use a bronchodilator this should be documented and the lack of bronchial hyper-reactivity after IMP administration documented.

Colistimethate sodium and placebo will be supplied in 30-vial packs.

Colistimethate sodium is supplied as sterile powder in a glass vial. Each vial contains 1,000,000 International Units (1 MIU) which weighs about 80 mg (equivalent to about 33 mg colistin base activity).

CONFIDENTIAL

Sponsor:	Zambon S.p.A.	Protocol Number:	Z7224L01
----------	---------------	------------------	----------

Identical sterile vials for placebo will be used. All vials will be masked with white plastic sleeves so that the contents are not visible. The weight of the powder is insignificant compared to the glass vial.

3.3 Study Schedule

The current trial will include 7 planned clinical visits at the investigational site, 1 telephone call 7 days after commencing treatment and 1 follow-up telephone call two weeks after discontinuation of treatment, as detailed in Section 8 of the CTP. A detailed flow chart of CTP Version 7.0 showing the procedures performed is given below in Table 3.3.1.

CONFIDENTIAL

Sponsor:	Zambon S.p.A.	Protocol Number:	Z7224L01
----------	---------------	------------------	----------

3.3.1 Trial Flow Chart

ACTIVITIES	Visit 1 Screening/ Rescreening	Visit 2 Randomisation	Phone call	Visit 3	Visit 4	Visit 5	Visit 6	Visit 7 EoT	Follow-up phone call	Exacer- bation Visit
	Within 30 Days of Visit 2	Day 0	Day 7	Day 28 ± 1 week	3 months ± 1 week	6 months ± 1 week	9 months ± 1 week	12 months ± 1 week	2 weeks ± 3 days after EoT	---
Informed consent	X									
Medical history/demography	X									
Verify eligibility for randomisation	X	X								
Previous/concomitant medications	X	X		X	X	X	X	X	X	X
AE monitoring including pulmonary exacerbations not otherwise reported	X	X	X	X	X	X	X	X	X	X
CCI training, dispensing/collection		X		X	X	X	X	X		
Pregnancy test	X	X		X	X	X	X	X		
Vital signs	X							X		X
Physical examination	X							X		X
12-lead ECG	X							X		
Obtain blood samples: Haematology and clinical chemistry/Renal Function	X			X ^a		X		X		
Collect sputum sample	X	X		X		X		X		X
Spirometry: FEV ₁ and FVC	X	X ^b		X	X	X	X	X ^b		X
CCI training, dispensing/collection		X						X		
Review of IMP administration & CCI use (adherence)		X	X	X	X	X	X	X		
Study medication: Dispense/accountability		X		X	X	X	X	X		
Record of hospitalizations and days of work absence due to pulmonary exacerbations			X	X	X	X	X	X		X

CONFIDENTIAL

Sponsor:	Zambon S.p.A.	Protocol Number:	Z7224L01
----------	---------------	------------------	----------

Weekly follow-up phone calls to determine end of pulmonary exacerbations										X
	a Renal function test only. b FEV ₁ and FVC to be measured pre-bronchodilator and 30 ± 10 minutes post-IMP dose.									

CONFIDENTIAL

Sponsor:	Zambon S.p.A.	Protocol Number:	Z7224L01
----------	---------------	------------------	----------

3.4 Concomitant Medication

Permitted concomitant medications are reported in Section 10 of the CTP.

3.5 Study Analysis Populations

There will be 4 analysis populations defined for the trial analyses:

3.5.1 Intention-To-Treat Population

The Intention-To-Treat Population (ITT) will include all subjects who provided informed consent and received a patient number (randomisation number) whether or not they receive IMP.

Following the ITT principle, subjects will be analysed according to the treatment they have been assigned to at randomisation.

3.5.2 Modified Intention-To-Treat Population

The modified ITT (mITT) Population will comprise all subjects who provided informed consent, were randomised and received at least 1 dose or partial dose of the IMP.

Subjects will be analysed according to the treatment they have been assigned to at randomisation.

The mITT will be used to produce summaries of baseline subject characteristics and for the analysis of all primary and secondary efficacy endpoints. Being a double-blind study, no bias due to the exclusion of the non-treated subjects is expected. Exposure variables will also be presented for the mITT.

In addition, the analysis of the mean annual NCFB pulmonary exacerbation rate and the [CCI] [redacted] will be performed on the subgroup of mITT subjects who were at least 80% adherent as recorded by the [CCI].

3.5.3 Safety Population

The Safety Population will comprise all subjects who provided informed consent, were randomised and received at least 1 dose or partial dose of IMP.

Subjects will be analysed according to the treatment they actually received.

The Safety Population will be used to produce summaries of all safety related endpoints and demography.

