18.4.1. TRIAL POPULATIONS

There will be 4 analysis populations defined for the trial analyses:

Intention-To-Treat (ITT) Population The Intention-To-Treat Population will include all subjects who provided informed consent and received a patient number (randomisation number) whether or not they receive IMP.

Modified Intention-To-Treat Population The Modified ITT (mITT) Population will comprise all subjects who provided informed consent, were randomised and received at least 1 dose or partial dose of the IMP.

Primary analyses will be performed on the mITT population with exclusions from the ITT defined and justified in the SAP.

Following the ITT principle, subjects will be analysed according to the treatment they have been assigned to at randomisation.

The mITT will be used to produce summaries of baseline subject characteristics and for the analysis of all efficacy variables.

Safety Population

The Safety Population will comprise all subjects who provide Informed Consent and received at least 1 dose or partial dose of IMP.

Subjects will be analysed according to the treatment they actually received.

The Safety Population will be used to produce summaries of all safety-related variables and demography.

Per-Protocol Population

The Per-Protocol Population (PP) will include all mITT subjects who were compliant with study drug administration (i.e. had a compliance of at least 80%) and who had no major protocol deviations that were considered as potentially impacting the efficacy results. Major protocol deviations might include, but are not limited to, subjects taking a non-permitted concomitant medication, the IMP not being administered during the trial as defined in the protocol, subjects receiving a treatment different than the one assigned by randomisation; others will be defined in the SAP.

Results of the primary and secondary efficacy analyses conducted in the PP will be considered as supportive.

Exclusion of subjects from the PP analyses will be decided jointly by the CRO and Sponsor's Medical Monitor, Clinical Trial Manager and Statistician prior to unblinding of the randomisation code and database release.

The subjects or observations to be excluded, and the reasons for their exclusion will be documented and approved by the above-mentioned persons prior to database release. The documentation will be filed together with the remaining trial documentation.

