4.1.1 Populations for the Analysis

Demographics and baseline characteristics will be summarised for the mITT population. Demographics and selected baseline characteristics will be also presented for the Safety Population.

The following baseline characteristics will be presented on the mITT Population only:

- Smoking and Alcohol Status
- Non-CF Bronchiectasis History
- Past and Concomitant Relevant Diseases, Diagnosis or Surgeries
- Prior and Concomitant Medication

No baseline testing will be performed.

Primary and relevant secondary efficacy variables will be summarised and analysed for the mITT and PP Population. Results on PP will be considered as supportive.

The number of days of work absence and hospitalisations will be analysed for the mITT population only.

In addition, the analysis on the mean annual NCFB pulmonary exacerbation rate and the CCI will be performed considering the subgroup of mITT subjects who were considered adherent i.e. had an adherence of at least 80% (excluding partial doses of $\leq 12.5\%$ as detailed in Section 4.5.1).

The exposure data will be analysed on the Safety and mITT Populations.

The safety variables will be summarised for the Safety Population.

In case an error occurs in treatment allocation, the following rule will be followed:

- If a subject was randomised but received the incorrect treatment for all the time the subject was in the study, he/she will be reported under the randomised treatment group for all analyses performed on the ITT and on the mITT Population (and in listings on all screened subjects). He/she will be reported under the treatment actually received for

CONFIDENTIAL

Sponsor:	Zambon S.p.A.	Protocol Number:	Z7224L01
----------	---------------	------------------	----------

all analyses performed on the Safety Population (i.e. an as-treated analysis will be performed). Such subjects will be excluded from the PP Population.

- If a subject received the incorrect treatment after being treated with the correct one, it's foreseen that the subject will be withdrawn from the study. Data for this subject will be analysed until the date of the wrong treatment dispensing. All the data collected after that date will be reported in listings and flagged, but not included in the summary statistics. He/she will be reported under the randomised treatment group for all analyses performed and listings presented.

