4.1.12 Listings

All data collected will be presented in the listings.

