4.10 Protocol Deviations

4.10.1 Major Protocol Deviation Criteria

Exact definitions of major protocol deviations affecting safety and efficacy analyses will be discussed at the blind review meeting and documented in the Blind Data Review and Analysis Sets Report. The Protocol Deviation and Non-Compliance Management Plan documents the process for identifying protocol deviations that would potentially exclude subjects from the PP Population.

If major protocol deviations occur as outlined in the criteria below, then the data from complete individual subjects, individual visits or individual evaluations will be excluded from the population of analysis as indicated.

Exclusion of subjects or observations from the analyses will be decided jointly by the CRO and Sponsor's Study Team prior to unblinding of the randomisation code and database release.

The subjects or observations to be excluded, and the reasons for their exclusion, will be documented and approved by the above-mentioned persons prior to database release. The documentation will be filed together with the remaining trial documentation.

The number of subjects in each analysis population will be reported. Major protocol deviations excluding subjects from any particular population will be described, reporting the number of protocol violators for each criterion. All major protocol deviations will be listed and summarised for all screened subjects.

Major protocol deviations will be classified according to the following categories:

- Concomitant Medication / Administration of Prohibited Medication;
- Inclusion or Exclusion Criteria;
- Informed Consent / ICF not signed or signed late;
- Informed Consent / Other;

CONFIDENTIAL

Sponsor:	Zambon S.p.A.	Protocol Number:	Z7224L01
----------	---------------	------------------	----------

- Investigational Product / Incorrect IMP kit given to subject;
- Investigational Product / IMP Dosing;
- Investigational Product / IMP Storage;
- Investigational Product / Other;
- Met Withdrawal Criteria but was not Withdrawn;
- Patient Privacy (PP) / PP not signed;
- Patient Privacy / Other;
- Randomization / Mis-stratification;
- Randomization / Multiple Randomizations;
- Randomization / Other;
- Randomization / Randomized Not Treated;
- Randomization / Treated and Not Randomized;
- SAE not reported or reported late;
- Study Procedure / Missed procedure;
- Study Procedure / Other;
- Study Procedure / Site Staff Authorization, Delegation, Training;

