4.13 Changes in Conduct or Planned Analyses from the Protocol

Sections 2.2, 4.4.11, 4.7.5 and 4.7.6.3: The protocol incorrectly referred to the units for the determination of CCI [REDACTED] which have been reported as CCI [REDACTED] by the central laboratory.

Section 3.9: The rationale and results for a reassessment of the original sample size calculation are provided to explain the reduced target sample size and associated levels of power.

Section 4.7.4: The protocol states that the Negative Binomial Model will consider the log-time on study as offset. However, as specified in Section 4.1.7, NCFB Pulmonary Exacerbations analyses focus on the treatment period so log-time on treatment will be considered.

Section 4.7.6.1: The protocol states that CCI [REDACTED] = CCI [REDACTED]. For time-to-event endpoints, generally the + 1 is not included because this overestimates the time by 1 day for every event, therefore "+ 1" has been deleted.

Section 4.7.6.4: The protocol states that any episodes of pneumonia will be considered as severe pulmonary exacerbations. Any reported episodes of pneumonia which do not require intravenous antibiotics and/or hospitalisation will be data queried to amend the Preferred Term. However, any pulmonary exacerbation on the Pulmonary Exacerbation form of the eCRF that is linked to an adverse event with a Preferred Term of 'Pneumonia' but does not have any CCI [REDACTED] or CCI [REDACTED] will be assumed to be a severe NCFB pulmonary exacerbation.

Section 4.7.6.5: The protocol states that the CCI [REDACTED] total score will be computed and analysed. However, as recommended in the Manual Scoring Instructions CCI [REDACTED] only the CCI [REDACTED] domain scores will be presented and analysed.

There have been no other changes in analyses from those defined in the protocol.

CONFIDENTIAL

Sponsor:	Zambon S.p.A.	Protocol Number:	Z7224L01
----------	---------------	------------------	----------

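### SAP 3.5.3 adds a randomisation condition to the protocol's Safety Population without declaring it, so a subject dosed but not randomised would be left out of the safety summary tables

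*SAP*

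**What the plan says.** Protocol 18.4.1: "The Safety Population will comprise all subjects who provide Informed Consent and received at least 1 dose or partial dose of IMP". Subjects in this set are analysed by the treatment they actually received. In the same section the protocol does require randomisation for the mITT Population, so the two sets are defined by different conditions.

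SAP 3.5.3: "The Safety Population will comprise all subjects who provided informed consent, were randomised and received at least 1 dose or partial dose of IMP". Analysis is again by treatment received. The SAP's mITT Population (3.5.2) likewise covers consented subjects who "were randomised and received at least 1 dose or partial dose of the IMP".

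SAP 4.1.1: "The safety variables will be summarised for the Safety Population".

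SAP 4.10.1 includes this category in its list of major deviations: "Randomization / Treated and Not Randomized".

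SAP 4.13, after itemising its changes from the protocol: "There have been no other changes in analyses from those defined in the protocol". The Safety Population definition is not among the items.

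**The concern.** A safety set is meant to hold everyone exposed to the product. The protocol achieves this by making exposure, together with consent, the only test. The SAP narrows the set, and the subjects removed are those in a deviation category that the SAP itself provides for. For any such subject, treatment-emergent events, laboratory values, ECG and spirometry would be missing from the by-treatment summaries.

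The change is also unexplained. The SAP does justify one exclusion in 3.5.2, saying that leaving out untreated subjects should not cause bias in a double-blind trial. That reasoning concerns subjects who received no dose and gives no ground for leaving out subjects who did. Section 4.13 is detailed enough to record the removal of one day from a time-to-event formula, so a reader would take its closing statement as complete. On this point it is not.

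**Working it through.** No figure in the plan depends on this, so the check is one of set membership followed by a count of the tables affected.

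**Step 1. Membership.** Take a subject who consented, was not randomised and received at least one dose.

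| Set | Conditions | In the set? |
|---|---|---|
| Protocol Safety (18.4.1) | consent, dosed | Yes |
| SAP Safety (3.5.3) | consent, randomised, dosed | No |
| ITT (SAP 3.5.1) | consent, randomisation number | No |
| mITT (SAP 3.5.2) | consent, randomised, dosed | No |
| PP (SAP 3.5.4) | mITT, adherent, no relevant major deviation | No |
| All screened (SAP 3.5.5) | consent | Yes |

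Under the SAP wording the Safety and mITT Populations have the same members. They differ only in whether a subject is counted under treatment received or treatment assigned.

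**Step 2. Is the case covered elsewhere?** SAP 4.1.1 has two rules for treatment errors. The first begins "If a subject was randomised but received the incorrect treatment for all the time the subject was in the study". The second concerns a subject who received the wrong treatment after the correct one. Neither deals with a subject who was never randomised.

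**Step 3. Tables affected.** In SAP 5.3.4 the tables naming the Safety Population are:

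- adverse events, 14.3.1.1 to 14.3.1.4: 1 + 6 + 2 + 1 = 10
- spirometry: 2
- vital signs: 3
- physical examination: 2
- ECG: 2
- haematology and clinical chemistry: 4
- Tables 14.3.4.6.1 and 14.3.4.6.2: 2

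The sum is 10 + 2 + 3 + 2 + 2 + 4 + 2 = 25. SAP 5.3.1 adds four more on the Safety Population: 14.1.4.2 (demographics), 14.1.10.1 (inhaled doses), 14.1.11.1 (exposure) and 14.1.13.1 (IMP interruptions). The subject is absent from 25 + 4 = 29 tables.

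**Step 4. Where the subject remains.** Tables 14.3.2.1 to 14.3.2.3 (deaths, SAEs, events leading to discontinuation) are listings with no population named. SAP 4.1.12 says "All data collected will be presented in the listings", which covers the adverse event and laboratory listings in 5.4. SAP 4.10.1 has major deviations listed and summarised for all screened subjects, and Table 14.1.2.2 runs on that set.

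**The case against.** The strongest reply is that the case is remote. Protocol 8.2 treats randomisation in the IWRS and kit assignment as one step, listed before the supervised first dose. Protocol 11.1 routes IMP allocation through the IWRS, and 11.3 has every consented subject entered there. In normal conduct, receiving IMP implies having been randomised, and on that view the SAP only spells out what the protocol takes for granted. The deviation category is one entry in a long classification list that may be amended, so it does not show that anyone expected or saw such a subject. This stands as an argument about frequency. It does not reconcile the two definitions, and it does not make the closing statement in 4.13 correct.

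A reader might infer that the subject's safety data would disappear from every safety table, or from the report. The documents do not support that: deaths, SAEs and events leading to discontinuation have their own listings without a population restriction, all collected data are listed, and the deviation itself would be summarised. The loss is confined to the population-based summaries.

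A reader might also infer a handful of affected subjects among the 377 randomised (SAP 3.9). No such number is given, and a subject who was not randomised cannot be one of the 377.

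Nor would an actual exclusion go unrecorded. SAP 4.10.1 requires excluded subjects and the reasons to be documented and approved before unblinding. What is undeclared is the change of definition.

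**Conclusion.** The inconsistency is real and minor. Two governing documents define the Safety Population differently, and the SAP's record of changes says otherwise. For each consented, dosed, non-randomised subject, data would be missing from 25 safety summary tables and four demography and exposure tables, while remaining in the listings and deviation summaries. The number of such subjects is not in the documents and may be zero, in which case the two definitions give identical tables. The primary efficacy analysis is unaffected: both documents run it on the mITT Population, which requires randomisation in each.

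The conclusion assumes that the table titles in SAP 5.3 will be applied as written, and that the blind data review did not decide separately how such a subject would be reported. That review's report is not among the documents.

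**What to change.** Delete the randomisation condition from SAP 3.5.3 so that it matches protocol 18.4.1, and add to the treatment-error rules in 4.1.1 that a subject treated without randomisation is reported under the treatment actually received. In text this is a few words.

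SAP Addendum 2.2 says that the database is locked and the trial unblinded, so the working remedy belongs in the trial report:

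- State how many treated, non-randomised subjects there were.
- If the number is zero, say so. That sentence settles the point, and no table is rerun.
- If it is above zero, add these subjects to the safety summaries, which means rerunning the Safety Population tables, and mark this as a change made after unblinding, as SAP section 1 requires.
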